9.7 Figures

The study specific figures are displayed in Table 13.

Table 13. Clinical study RPL554-COV-201 Figures.

Figure #	Figure Name
1	Patient disposition (adapted from the Consort Statement).
2	Kaplan–Meier plot of time to Recovery, ITT.
3	Histogram of ordinal scores at Day 7, 14, 29 by treatment group and baseline ordinal scale, ITT.
4	Proportion of patients in oxygen need by day in study.

pg. 27 Confidential

10 LISTINGS

Data is presented on a by-patient basis in this section. The study specific listings are displayed in Table 14. The following categories apply to the listings:

- 16.2.1 Patient Dispositions, Patient Eligibility
 - Listing of disposition: It should be clear which patients discontinued the study early, their study treatment, when they discontinued and the reason;
 - Listing of visit dates
 - Listing of eligibility: e.g. confirmation patients met the inclusion/exclusion criteria
- 16.2.2 Protocol Deviations
 - Listing of all patients with protocol deviations, with the deviation specified.
- 16.2.3 Study Populations
 - Listing of patients and whether they are included in each population;
 - o Listing of patients excluded from key population(s) e.g. the efficacy population
- 16.2.4 Demographic and Baseline Characteristic Data
 - Listing of demographics;
 - Listing of other baseline data (e.g. COVID disease severity; brief physical examination findings; medical history; hospital admission information)
 - Listing of prior and concomitant medications
- 16.2.5 Compliance with study medication
- 16.2.6 Individual Efficacy Data Listing of efficacy data
- 16.2.7 Adverse Event Listings Listing of all adverse event information
- 16.2.8 Laboratory Safety Tests Listings of all laboratory data.
- 16.2.9 Vital Signs, Physical Findings and Other Observations

Table 14. Clinical study RPL554-COV-201 Listings.

Listing Name	Listing Contents
Completed/Discontinued	A patient listing of analysis population eligibilities.
Patients	
Protocol Deviations	All patient-specific protocol deviations and non-patient specific protocol deviations.
Patients Excluded from	A listing of patients overall.
Analysis Sets	
Analysis Population	A listing of patients by Treatment Group.
Inclusions/Exclusions	
Patients who Early	A listing of patients by Treatment Group who discontinued dosing or
Terminated or Discontinued	terminated study follow-up and the reason.
Treatment	
Patient-Specific Protocol	A listing of patients by Treatment Group.
Deviations	
Non-Patient-Specific	A listing of deviations.
Protocol Deviations	

pg. 28 Confidential

Listing Name	Listing Contents	
Baseline Demographic	Individual listings for all demographic information by Treatment	
Characteristics	Group.	
Baseline Disease	Individual listings for all baseline COVID information by Treatment	
Characteristics	Group.	
Baseline Medical History	Individual listing for all co-morbid conditions and surgical history by	
	Treatment Group.	
Baseline Brief Physical	Individual listing by Treatment Group.	
Exam Findings		
Study Medication	Individual listings for all patients who received at least at least one	
Compliance for each study	dose of study medication, including the number of days taken and	
day	number of doses received; and for all patients who discontinued	
	dosing, missed doses, or halted or slowed doses	
7-point ordinal scale score at	Individual listing by Treatment Group.	
baseline and for each study		
day		
Vital signs at baseline and	Individual listing by Treatment Group.	
for each study day		
Prior and Concomitant	Individual listings of medications that were started prior to dosing and	
Medications at baseline and	continuing at the time of dosing by Treatment Group (those listed in	
for each study day	the concomitant medication list as: Other (and comments), Medical	
	History or Adverse Event).	
Medications for the	Individual listing by Treatment Group (those listed in the concomitant	
Treatment of COVID-19	medication list as: Treatment of COVID-19).	
(Standard of Care) at	Medication classes:	
baseline and for each study	Angiotensin converting enzyme inhibitors (ACE inhibitors),	
day	Angiotensin II receptor blockers (ARBs),	
	3. Antibiotics,	
	4. Antifungal agent,	
	5. Antiviral agent,	
	6. Corticosteroid,	
	7. Immunosuppressant agents (not oral steroids),	
	8. Intravenous fluids,	
	Non-steroidal anti-inflammatory (NSAIDs), Oral/orogastric fluids,	
	11. Other targeted COVID-19 medications (comments)	
Treatment or Therapy for	Individual listings for all standard of care COVID-related	
COVID-19 (Standard of	treatments/therapies (excluding medications) received while	
Care) at baseline and for	hospitalized and the duration.	
each study day	nospitalized and the duration.	
Standard of Care Laboratory	Individual listings for all standard of care laboratory results while	
Test Results at baseline and	hospitalized.	
for each study day	noophanzoa.	
New respiratory illness or	Individual listing by Treatment Group	
other illness during	That vidual nothing by Troutmont Group	
hospitalization		
Listing of Non-Serious	Individual listing by Treatment Group.	
Adverse Events	,	
Safety Laboratory Results at	Individual listing by Treatment Group.	
screening and discharge	······································	
Listing of Death and Other	Individual listing by Treatment Group.	
Serious Adverse Events	······································	
Pregnancy Reports Individual listing by Treatment Group.		
griding i toporto		

pg. 29 Confidential

11 REPORTING CONVENTIONS

P-values will be reported to 3 decimal places; p-values less than 0.0005 will be reported as "<0.001" and p-values greater than 0.9995 will be reported as ">0.999".

The mean, standard deviation, and other statistics will be reported to 1 decimal place greater than the original data. The minimum and maximum will use the same number of decimal places as the original data.

Proportions will be presented as 2 decimal places; values greater than zero but <0.005 will be presented as "<0.01".

Estimated parameters, not on the same scale as raw observations (e.g. regression coefficients) will be reported to 3 significant figures.

12 TECHNICAL DETAILS

Additional summaries/data points may be included in the final version of a table, figure, or listing.

Additional tables, figures, and listings may be generated to supplement the planned output.

pg. 30 Confidential

14 EXAMPLE SHELLS

pg. 32 Confidential

Table 14.1.1 Patient Disposition

Patient Disposition Enrolled Ensifentrine Placebo (N=45) (N=30) (N=15)

Completed Day 7

Completed Day 14

Completed Day 29

Completed post-Discharge Follow-up (outpatient)

Completed D29 post Follow-up (outpatient)

Completed D60 post Follow-up (outpatient)

Withdrawal

Reason of withdrawal

Adverse Event

Death

Lost to follow up

Pregnancy

Protocol Violation

Physician Decision

Study Termination by Sponsor

Withdrawal by Patient

Other

Change of Consent by Patient - Reconsent (withdrawl from study medication, continued in follow-up)

Total number screened: 122 (77 failed screen)

Discharge=The patient is discharged and leaves the hospital alive.

Eligible patients were randomized within 4 days of hospital admission.

Randomized patients received study medication until hospital discharge or up to 29 days of treatment, whichever was first.

Completed Day 7=patient randomized and hospitalized taking study medication for ≥7 days.

Completed Day 14= patient randomized and hospitalized taking study medication for ≥14 days.

Completed Day 29= patient randomized and hospitalized taking study medication for 29 days.

Discharge f/u= 4-10 days after hospital discharge.

Day 29 f/u = 26-32 days following receipt of 1st dose of study medication for telephone review of the 7-point ordinal scale, need for re-hospitalization and vital status

Day 60 f/u = 55-65 days following receipt of 1st dose of study medication for telephone review of the 7-point ordinal scale, need for re-hospitalization and vital status

pg. 33 Confidential

Table 14.1.2: Screen Failures

Reasons Patients were Screened but not Enrolled	N (%)
Investigator decision - patient unsuitable to participate	
Creatinine clearance < 30 mL/min at screening	
Participation in any other clinical trial	
Evidence of multiorgan failure	

pg. 34 Confidential

Table 14.1.3: Major Protocol Deviations

pg. 35 Confidential

Table 14.1.4: Analysis Sets

	Enrolled (N=45)	Ensifentrine (N=30)	Placebo (N=15)
Number Randomized			
Number iTT			
Number Per Protocol			
Number Safety Set			

pg. 36 Confidential

Table 14.1.5: Baseline Demographic Characteristics

		Enrolled	l Ensifentrine	Placebo
Baseline Demo	ographic Characteristics	(N=45)	(N=30)	(N=15)
Age	Mean, Years (SD) Median (min, max)			
Gender	Female Male			
Height	Height (cm) (SD)			
Weight	Weight (kg) (SD)			
ВМІ	BMI (kg/m²) (SD)			

Pulse Rate/Heart Rate	beats per minute			
Respiratory Rate	beats per minute			
Blood Pressure (SBP)	mmHg			
Blood Pressure (DBP)	mmHg			
Arterial Blood Pressure	mmHg			
Oxygen Saturatior	n SPO2			
Supplemental Oxygen	FiO2			
Co-morbid conditions	None			
-	One Two or more			

pg. 40 Confidential

Baseline Clinical	Characteristic	s Mean (SD) or Count %		l Ensifentrine (N=30)	Placebo (N=15)
		moun (OD) or Count 70	n	n	n
Obesity	Yes No				
Hypertension	Yes No				
Diabetes Type 1	Yes No				
Asthma	Yes No				
COPD	Yes No				

FDA's document: COVID-19: Developing Drugs and Biological Products for Treatment or Prevention Guidance for Industry (May 2020).

- Mild disease (meeting all inclusion and no exclusion criteria): Symptoms of mild illness that could include fever, cough, sore throat, malaise, headache, muscle pain, gastrointestinal symptoms, without shortness of breath or dyspnea and no clinical signs indicative of moderate, severe, or critical severity.
- Moderate disease (meeting all inclusion and no exclusion criteria): could include any symptom of mild illness or shortness of breath with exertion. Clinical signs suggestive of moderate illness, such as respiratory rate ≥20 breaths per minute, saturation of oxygen (SpO2) > 93% on room air at sea level, heart rate ≥ 90 beats per minute and no clinical signs indicative of severe or critical severity.
- Severe disease (meeting all inclusion and no exclusion criteria): could include any symptom of moderate illness or shortness of breath at rest, or respiratory distress. Clinical signs indicative of severe systemic illness, such as respiratory rate ≥ 30 per minute, heart rate ≥ 125 per minute, SpO2 ≤ 93% on room air at sea level or PaO2/FiO2 < 300 and no criteria of critical severity.

pg. 41 Confidential

Table 14.1.9: Disease onset, ITT

		Enrolled (N=45)	Ensifentrine (N=30)	Placebo (N=15)
Days with COVID Symptoms before randomization	Mean (SD) Median (Min. – Max.)	N	N	n
Oxygen at Randomization	Yes No	N	N	n

pg. 42 Confidential

Table 14.1.10: Number and Proportion Taking Dexamethasone or Remdesivir, ITT

Overall, and by Treatment Group from initiation of study medication

		Enrolled (N=45)	Ensifentrine (N=30)	Placebo (N=15)
Taking Dexamethasone and Remdesivir	Yes No ^{&}		,	
Taking Dexamethasone only	Yes No			
Taking Remdesivir only	Yes No			

[&]No Dexamethasone and No Remdesivir

pg. 43 Confidential

^a All randomized participants reported 2-Moderate of COVID disease severity at baseline

Table 14.1.11: COVID-19 Treatment and other Concomitant Respiratory Medications, ITT

Medications Introduced from initiation of study medication

		Enrolled (N=45)	Ensifentrine (N=30)	Placebo (N=15)
Taking COVID-19 Treatment	Yes			•
	No			
Antibiotics	Yes			
	No			
Antiviral Agent	Yes			
-	No			
Corticosteroid	Yes			
	No			
Intravenous Fluids	Yes			
	No			
Non-steroidal Anti-inflammatory	Yes			
	No			
other	Yes			
	No			

pg. 44 Confidential

Table 14.2.1: Study Medication Compliance from initiation of study medication

		Enrolled	Ensifentrine Placeb		
		(N=45)	(N=30)	(N=15)	
Missed dose of study medication after	Yes				
administration of 1 st	No*				

^{*}No means 100% compliance Listing will have information for doses missed

pg. 45 Confidential

Table 14.2.2: Patient last day receiving study medication from initiation of study medication, by study day

	Study Day	Enrolled (N=45)	Ensifentrin e (N=30)	Placebo (N=15)
Patient final day receiving study medication	2			
	3			
	4			
	5			
	6			
	7			
	8			
	9			
	10			
	11			

Study day of when the patient was administered their last dose of study medication (post-1st dose on Day 1).

pg. 46 Confidential

Table 14.2.3: Proportion of Patients with Recovery* from initiation of study medication at 29 Days, ITT

		Ensifentrine (N=30)	Placebo (N=15)
Proportion Recovered (scored 1 or 2) at Day 29 Overall Analysis results		N	Ň
Proportion recovered by: Age Group	< 65 years old	N (XX%)	N
	> 65 years	Ň	N
Gender	Male	N	N
	Female	N	N
Disease Severity	Moderate	N	N
Smoking History	Present	N	N
	Previous	N	N
	Never	N	N
# of Co- morbidities	None	N	N
	One	N	N
	Two or more	N	N

n = number of patients with recorded value

pg. 47 Confidential

^{*} Recovery = one of the following two categories from the 7-point ordinal scale:

^{1.} not hospitalized, no limitations of activities;

^{2.} not hospitalized, limitation of activities, home oxygen requirement, or both.

Table 14.2.4: Proportion of Patients with Recovery* from initiation of study medication at 29 Days, PP

		Enrolled (N=45)	Ensifentrine (N=30)	Placebo (N=15)
Overall				
Patient with Recovery	Yes No			

^{*} Recovery = one of the following two categories from the 7-point ordinal scale: 1. not hospitalized, no limitations of activities;

Confidential pg. 48

^{2.} not hospitalized, limitation of activities, home oxygen requirement, or both.

Table 14.2.5: Time to recovery*, from initiation of study medication - Day 29 (or discharge, whichever was first)

p-value Enrolled Ensifentrine Placebo (log-(N=45) (N=30) (N=15) rank)

Days to recovery

Mean (SD)

Median (Min. - Max.)

n = number of patients with recorded value

pg. 49 Confidential

^{*} Recovery = one of the following two categories from the 7-point ordinal scale:

^{1.} not hospitalized, no limitations of activities;

^{2.} not hospitalized, limitation of activities, home oxygen requirement, or both.

Table 14.2.6: Proportion of patients in recovery* from initiation of study medication, ITT

		Enrolled (N=45)	Ensifentrine (N=30)	Placebo (N=15)
Recovery through Day 60	n			
	Yes			
	No			
Recovery Day 1 - Day 7	n			
	Yes			
	No			
Recovery Day 1 - Day 14	n			
	Yes			
	No			

n = number of patients with recorded value

^{*} Recovery = one of the following two categories from the 7-point ordinal scale:

^{1.} not hospitalized, no limitations of activities;

^{2.} not hospitalized, limitation of activities, home oxygen requirement, or both.

Table 14.2.7: Proportion of patients with improvement of one category using the 7-point ordinal scale from initiation of study medication, ITT

		Enrolled (N=45)	Ensifentrine (N=30)	Placebo (N=15)
One Category Improvement, Day 1 - Day 7	n	,	,	•
	Yes			
	No			
One Category Improvement, Day 1 - Day 14	n			
	Yes			
	No			
One Category Improvement, Day 1 - Day 29	n			
	Yes			
	No			

Improvement = A decrease from baseline of at least one point in the 7-point ordinal score (or discharge, whichever was first)

pg. 51 Confidential

Table 14.2.8: Proportion of patients with improvement of two categories using the 7-point ordinal scale from initiation of study medication, ITT

		Enrolled (N=45)	Ensifentrine (N=30)	Placebo (N=15)
Two Categories Improvement, Day 1 - Day 7	n	•		
	Yes			
	No			
Two Categories Improvement, Day 1 - Day 14	n			
	Yes			
	No			
Two Categories Improvement, Day 1 - Day 29	n			
. , ,	Yes			
	No			

Improvement = An increase from baseline of at least one point in the 7-point ordinal scale score (or discharge, whichever was first)

pg. 52 Confidential

Table 14.2.9: All-cause mortality, ITT

	Ensifentrine (N=30)	Placebo (N=15)
Reason of death at Day 29	0 (0%)	
Reason of death at Day 60	0 (0%)	

Table 14.2.10: Proportion of patients Alive and not in Respiratory Failure* from initiation of study medication, ITT

Proportion of Patients	Proportion of Patients Alive and not in		Placebo
Respiratory Failure (Scales less than 6)		(N=30)	(N=15)
Day 1 - Day 7	n		,
	Yes		
	No		
Day 1 - Day 14	n		
-	Yes		
	No		
Day 1 - Day 29	n		
-	Yes		
	No		

pg. 54 Confidential

⁽or discharge, whichever was first)
*7-point ordinal scale score = 1, 2, 3, 4 or 5. n = number of patients with recorded value

Table 14.2.11: Summary of Proportion of patients re-hospitalized following initiation of study medication and subsequent discharge (over 60 days), ITT

Proportion of Patients	Re-hospitalized	Enrolled (N=45)	Ensifentrine (N=30)	Placebo (N=15)
Day 1 - Day 60	ay 1 - Day 60 n			
	Yes			
	No			

n = number of patients with recorded value

Table 14.2.12: Duration of hospitalization from initiation of study medication (Day 1 - Day 29 (or discharge, whichever was first); measured in days), ITT

Days of hospitalization	Enrolled		Placebo p-value*
from Day 1	(N=45	(N=30)	(N=15)
Median (Q1 - Q3)			

^{*}Wilcoxon rank sum test

Hospitalized = # days where the 7-point ordinal scale score = 3, 4, 5 or 6.

Discharge = The patient is discharged and leaves the hospital alive.

pg. 56 Confidential

Table 14.2.13: Change from Baseline in 7-point Ordinal Scale at Days 7, 14, and 29, ITT

Change from 7-point Ordin	n Baseline in nal Scale	Enrolled (N=45)	Ensifentrine (N=30)	Placebo (N=15)
Day 7	n Mean (SD)	()	()	()
Day 14	n Mean (SD)			
Day 29	n Mean (SD)			

Computed from Day 1 scale minus Day 7, Day 14, and Day 29 scale accordingly (or discharge) (or discharge, whichever was first)

pg. 57 Confidential

Table 14.2.14: Total time on Supplemental Oxygen (Day 1 - Day 29; measured in days), ITT

Days of Suppl	emental Oxygen	Enrolled	Ensifentrine	Placebo
(Scale=4)		(N=45)	(N=30)	(N=15)
Day 1 - 29	Median (Q1 - Q3)			

Hospitalized patient: 7-point ordinal scale score = 4, 5, or 6. Or 7-point ordinal scale score is equal to 7 if patient dies while hospitalized between Day 1-29.

Not hospitalized patient supplemental oxygen = # days where the 7-point ordinal scale score is equal to 2 (if required to have home oxygen).

pg. 58 Confidential

Table 14.2.15: Total time of non-invasive ventilation or high flow oxygen use (post-dose Day 1 - Day 29 (or discharge, whichever was first); measured in days)

Days of non-invasive ventilation or High Flow Oxygen Use (Scale=5)		Enrolled (N=45)	l Ensifentrine (N=30)	Placebo (N=15)
Day 1 - 29	Median (Q1 - Q3)			

Non-invasive ventilation or high flow oxygen use = # days where the 7-point ordinal scale score is equal to 5 or 6. Or 7-point ordinal scale score is equal to 7 if patient dies while hospitalized between Day 1-29.

pg. 59 Confidential

Table 14.2.16: Summary of the Proportion of Patients Alive and with Oxygen Use at Days 7, 14 and 29 (or discharge, whichever was first), ITT

Proportion of Patie Oxygen Use (Scale		Enrolled (N=45)	Ensifentrine (N=30)	Placebo (N=15)
Day 7	Yes No		,	
Day 14	Yes No			
Day 29	Yes No			

Hospitalized patient supplemental oxygen = the 7-point ordinal scale score is equal to 4, 5, or 6. Not hospitalized patient supplemental oxygen = the 7-point ordinal scale score is equal to 2 (if required to have home oxygen).

pg. 60 Confidential

Table 14.2.17: Summary of the Proportion of Patients Alive and with non-invasive Ventilation or High Flow Oxygen Use at Days 7, 14 and 29 (or discharge, whichever was first), ITT

Proportion of Patier Ventilation or High (Scale=5)	nts with Non-invasive Flow Oxygen Use	Enrolled (N=45)	Ensifentrine (N=30)	Placebo (N=15)
Day 7	Yes No			
Day 14	Yes No			
Day 29	Yes No			

Non-invasive ventilation or high flow oxygen use = the 7-point ordinal scale score is equal to 5 or 6.

pg. 61 Confidential

Table 14.2.18: Proportion of Patients Alive and Receiving Invasive Mechanical Ventilation or Extracorporeal Membrane Oxygenation (ECMO, 7-point ordinal scale criteria #6) at Days 7, 14 and 29 (or discharge, whichever was first), ITT

Proportion of Patier (Scale=6)	nts with ECMO	Enrolled (N=45)	Ensifentrine (N=30)	Placebo (N=15)
Day 7	Yes No			
Day 14	Yes No			
Day 29	Yes No			

IMV = The 7-point ordinal scale score is equal to 6.

Table 14.3.1: Time to first composite AE

		Enrolled (N=45)	Ensifentrine (N=30)	Placebo (N=15)
Proportion of AE	Yes No			
Time to first composite AE ^a	Days from consent (SD) Median (min Max.)			

^a Consider those who experienced Adverse events

Table 14.3.2: Number/Proportion Treatment emergent adverse events

	Statistic	Total	Ensifentrine (N=30)	Placebo
TEAE Category			` ,	(N=15)
Any TEAE	N (%)			
Any TEAE leading to study medication discontinuation Any TEAE related to study medication				
Any serious TEAE				
Any serious TEAE leading to study medication discontinuation Any serious TEAE leading to death				
Any TEAE classified by maximum severity				
Mild				
Moderate				
Severe				
Any serious TEAE classified by maximum severity				
Moderate				
Severe				

Abbreviations: AE, adverse event; N, number of patients in treatment group; n, number of patients in analysis; TEAE, treatment-emergent adverse event; %, percentage of patients calculated relative to the total number of patients in the treatment group.

TEAEs were defined as all AEs that started after the first dose of study treatment or started after the first dose of study treatment or started prior to first dose of study treatment and worsened, based on the Investigator's assessment of severity on or after the first dose of study treatment. TEAEs with a missing severity were classified as severe

pg. 64 Confidential

Table 14.3.3: Number/Proportion TEAEs by System Organ Class and Preferred Term

	Statistic	Total	Ensifentrine (N=30)	Placebo (N=15)
System Organ Class Preferred Term			(11 00)	(11 10)
Patients with at least one TEAE	N (%)			
Metabolism and nutrition disorders	N (%)			
Dehydration, hyperglycemia	N (%)			
Gastrointestinal disorders				
Diarrhoea				
Investigations	N (%)			
Alanine aminotransferase increased, Aspartate aminotransferase increased	N (%)			
Vascular disorders	N (%)			
Hypertension	N (%)			
Shock	N (%)			

n = number of patients

Table 14.3.4: Number/Proportion TEAEs Leading to Discontinuation of Study by System Organ Class and Preferred Term

Table 14.3.5: Number/Proportion TEAEs Causally Related to the Study Treatment by System Organ Class and Preferred Term

pg. 65 Confidential

Table 14.3.6: Number/Proportion TEAEs by Maximum Severity by System Organ Class and Preferred Term

System Organ Class	Severity	Statistic	Total	Ensifentrine (N=30)	Placebo (N=15)
Preferred Term Patients with at least one TEAE	Severe	N (%)			
	Moderate Mild	N (%) N (%)			
SOC	Severe				
	Moderate				
	Mild				
Preferred Term	Severe				
	Moderate				
	Mild				

Table 14.3.7: Number/Proportion Serious TEAEs by System Organ Class and Preferred Term

Table 14.3.8: Number/Proportion Serious TEAEs Causally Related to the Study Treatment by System Organ Class and Preferred Term

Table 14.3.9: Number/Proportion Serious TEAEs by Maximum Severity by System Organ Class and Preferred Term

Table 14.3.10: Number/Proportion Serious TEAEs Leading to Discontinuation of Study by System Organ Class and Preferred Term

Table 14.3.11: Number/Proportion Serious TEAEs with an Outcome of Death by System Organ Class and Preferred Term

Exploratory Analyses

ECMO: invasive mechanical ventilation or extracorporeal membrane oxygenation

Description of the distribution of the 7-point ordinal scale outcomes using plots (e.g., stacked bar plots representing the proportion of patients in each category, by treatment arm, over time).

Descriptive summary of the number of days between hospital admission, positive PCR test (or as per hospital testing protocol) and randomization.

[figure not shown]
Proportion of total patients requiring any oxygen at randomization.

- For those that required oxygen, the mean/standard deviation or median/IQR for the oxygen amount (in FiO2).
- Oxygen use while hospitalized and undergoing study treatment.

Measurement of the oxygen requirement: compare the oxygen requirement (mean and median) for each arm using daily supplemental oxygen flow (L/min).

Figures

Figure 1: Patient Disposition

pg. 68 Confidential

Figure 2: Kaplan–Meier plot of time to Recovery

pg. 69 Confidential

Figure 3: Histogram of ordinal scores at Day 7, 14, 29 by treatment group and baseline ordinal scale

Figure 4: Proportion of Patients in Oxygen Need by Day in Study

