7.2 Endpoints

Clinical study endpoints and associated definitions are listed in Table 5. Additional definitions are included in Section 8. Analysis tables are included in Section 9.3, Section 9.4 and Section 9.5.

Table 5. Clinical study RPL554-COV-201 endpoint definitions.

Endpoints	•	Definitions
Primary Refer to Section 9,	The proportion of patients who are in recovery state at Day 29.	Clinical status assessed using the 7-point ordinal scale score.
Table 10		The proportion of patients in each treatment arm that meet the definition of recovery.
		Recovery = one of the following two categories from the 7-point ordinal scale: 1. not hospitalized, no limitations of activities; 2. not hospitalized, limitation of activities, home oxygen requirement, or both.
Secondary Refer to Section 9,	Time to a recovery state (Day 1-Day 29; measured in days)	Clinical status assessed using the 7-point ordinal scale score.
Table 11		Time to recovery = elapsed time (in days) from Day 1 to the first day on which patients satisfy either 1 or 2 category listed in the primary endpoint.
	Proportion of patients who are in a recovery state at Days 7, 14 and 60.	Clinical status assessed using the 7-point ordinal scale score.
		The proportion of patients in each treatment arm that meet the definition of recovery.
		Recovery = one of the following two categories from the 7-point ordinal scale:

pg. 14 Confidential

Endpoints		Definitions
		not hospitalized, no limitations of activities; not hospitalized, limitation of activities, home oxygen requirement, or both.
	Proportion of patients with improvement of one category using the 7-point ordinal scale	Clinical status assessed using the 7-point ordinal scale score.
	(Day 1 - Days 7, 14 and 29).	The proportion of patients in each treatment arm that meet the definition of a one category improvement in clinical status.
		Improvement in clinical status = a decrease from baseline of one point in the 7-point ordinal score (eg, 5 to 4).
	Proportion of patients with improvement of two	Clinical status assessed using the 7-point ordinal scale score.
	categories using the 7-point ordinal scale (Day 1 - Days 7, 14 and 29).	The proportion of patients in each treatment arm that meet the definition of a two category improvement in clinical status.
		Improvement in clinical status = a decrease from baseline of two points in the 7-point ordinal score (eg, 5 to 3).

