9.4 Secondary Endpoint Analysis

Patients that die in the study will be handled as worst case in all analyses.

To have an evaluation using all patients we will count an event as the type of need or worse (eg, patients with oxygen need; non-invasive ventilator need; ventilator need; or with death at time of evaluation will be counted as having data supporting oxygen need), and included in both denominator and numerator (refer to Section 8.5).

9.4.1 Time to a recovery state (Day 1 - Day 29; measured in days)

The time to recovery from Day 1 to Day 29 will be compared between treatment groups using a log-rank test; patients not in recovery at end-of study/withdrawal will be censored at last observed time point in the treatment period or at last time status was assessed if collected post treatment-withdrawal. Patients with death as outcome will be censored at the scheduled end-of-study Day 29. Data will be illustrated using Kaplan-Meier plots and the median time to recovery estimated if appropriate. Stratification in the model with respect to COVID disease severity will be done if the randomization outcome has sufficient numbers in each group with respect to these characteristics.

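### Shell Table 14.2.5 sets an uncensored mean and median of days to recovery beside a log-rank p-value, so its descriptive figures can understate the difference that the test compares

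*SAP*

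**What the plan says.** SAP Table 5 (section 7.2) defines the endpoint: "Time to recovery = elapsed time (in days) from Day 1 to the first day on which patients satisfy either 1 or 2 category". A patient who never reaches score 1 or 2 has no such day.

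SAP 9.4.1 handles those patients by censoring. For deaths: "Patients with death as outcome will be censored at the scheduled end-of-study Day 29". For the rest: "patients not in recovery at end-of study/withdrawal will be censored at last observed time point in the treatment period", or at the last status assessment if one was made after treatment withdrawal. The arms are compared by log-rank test. For estimation the section says only: "Data will be illustrated using Kaplan-Meier plots and the median time to recovery estimated if appropriate". It names no hazard ratio and no difference between arms.

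In the SAP's example shells (section 14), Table 14.2.5 is titled "Time to recovery*, from initiation of study medication - Day 29 (or discharge, whichever was first". Its rows under days to recovery are Mean (SD) and "Median (Min. - Max", next to a log-rank p-value column. The footnote is "n = number of patients with recorded value". The shell has no row for number recovered, number censored, deaths, Kaplan-Meier median or confidence interval. SAP Table 11 marks most secondary tables as ITT but not this one.

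**The concern.** A simple mean or median of partly censored times does not estimate what a log-rank test compares. If only recovered patients contribute, an arm with more deaths or unresolved stays loses its worst patients from the average, and the table can show similar days in both arms beside a small p-value.

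This matters more than a layout slip usually would, because 9.4.1 plans no effect measure and makes the Kaplan-Meier median conditional. The shell's mean and median are then the only numerical summaries assured for the first-listed secondary endpoint. The trial is unpowered (SAP 8.1), and SAP 8.2 sees its use as informing later studies about the treatment effect. A planner who takes the days from this table could take too small a difference.

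**Working it through.** The plan gives no recovery rate, effect size or power for this endpoint, so there is no figure to reproduce. From the documents come the arm sizes (30 and 15), the Day 29 horizon and the 9.4.1 censoring rules. **All recovery rates and day values below are assumptions.**

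**1. What a recorded value could mean.** The shell does not define it. Two points favour recovered patients only. The Table 5 definition yields a value only on recovery. The comparable time-to-event shell, Table 14.3.1, is explicitly limited to patients with the event. Against that, the same footnote sits under Tables 14.2.6, 14.2.10 and 14.2.11, whose Yes/No rows include patients without the event. Both readings are checked.

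**2. Recovered only, simple arithmetic.** Let p be the proportion recovered by Day 29 and m the mean days among them. With non-recovered patients counted to Day 29, the mean is p × m + (1 − p) × 29. Take m = 9 in both arms:

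- p = 0.95: 0.95 × 9 + 0.05 × 29 = 10.0
- p = 0.90: 0.90 × 9 + 0.10 × 29 = 11.0
- p = 0.80: 0.80 × 9 + 0.20 × 29 = 13.0

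The shell would show 9 v 9 each time. The all-patient figures differ by 3.0 days (95% v 80%) or 2.0 days (90% v 80%).

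**3. Recovered only, 30 v 15 patients.** Recovered patients take 3, 5, 7, 9 or 11 days in equal numbers. All others are censored at Day 29. The restricted mean is the area under the Kaplan-Meier curve to Day 29.

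| Recovered, ensifentrine v placebo | Mean, recovered only | Restricted mean | Log-rank p |
|---|---|---|---|
| 30/30 v 10/15 | 7.0 v 7.0 | 7.0 v (10 × 7 + 5 × 29)/15 = 14.3 | 0.014 |
| 25/30 v 5/15 | 7.0 v 7.0 | (25 × 7 + 5 × 29)/30 = 10.7 v (5 × 7 + 10 × 29)/15 = 21.7 | 0.003 |

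The recovered-only median is also 7 v 7 in both rows. In the first row the Kaplan-Meier medians are 7 v 9 days. In the second the placebo median is not reached.

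**4. How typical zero is.** Simulations with 30 v 15 patients:

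- Equal speed, recovery 95% v 85%, 95% v 70% and 90% v 50%: recovered-only mean differences of −0.01, 0.04 and −0.01 days, against restricted-mean differences of −2.1, −5.1 and −8.1.
- Proportional hazards (placebo median 7, 10 or 13 days; recovery hazard ratio 1.5 or 2.0): the recovered-only difference is 24% to 54% smaller than the restricted-mean difference. At median 10 and ratio 1.5 it is −1.8 against −3.4 days.

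In the constructed layout with equal speed and equal recovery (28/30 v 14/15; recovered patients evenly spread over Days 4 to 10), nothing is hidden: every difference is 0 and p = 1.0.

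**5. Censored days counted as values.** The 30/30 v 10/15 example then gives means of 7.0 v 14.3 and medians of 7 v 9, so the difference stays visible. The fault moves to early losses. If one of the five non-recovered placebo patients is lost on Day 4, the simple mean is (70 + 4 × 29 + 4)/15 = 12.7. Under Kaplan-Meier, with that patient censored on Day 4, the curve steps to 13/15 = 0.867 at Day 3, then 0.722, 0.578, 0.433 and 0.289 at Days 5, 7, 9 and 11. The restricted mean is 3 × 1 + 2 × (0.867 + 0.722 + 0.578 + 0.433) + 18 × 0.289 = 13.4 days.

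**The case against.** A reader might infer that non-recovered patients and deaths drop out of this endpoint, or that a real difference will be reported as zero. The documents support neither. Those patients stay in the log-rank test printed in the same table and in Figure 2 (Kaplan-Meier, ITT). They also stay in the recovery proportions (Tables 14.2.3 and 14.2.6), the mortality table (14.2.9) and duration of hospitalization (Table 14.2.12). As defined in SAP Table 5, duration of hospitalization counts every day at scores 3 to 6, and score 7 for in-hospital death. Zero needs equal speed among recovered patients, and the shell has no difference cell.

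The recovered-only restriction is itself an inference: the footnote does not state it, and Table 14.3.1 shows that the SAP can say so when it means it. The shells are examples, and SAP section 12 allows added summaries. Other shells hint at few non-recovered patients: Table 14.2.2 lists last dosing days only up to Day 11, and Table 14.2.9 carries 0 (0%) deaths for ensifentrine. These are hints, not data. The endpoint is secondary in a trial whose analyses are all exploratory.

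All of this limits the point, but does not remove it. The SAP preface presents the sample tables as planned for the final analyses. The shell names a mean that 9.4.1 does not plan, and it gives a misleading summary under either reading. Permission to add rows does not correct those already there.

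**Conclusion.** The point holds as a mismatch between SAP 9.4.1 and Table 14.2.5, confined to that table's descriptive figures. The test and its censoring rules are not in question. On the likelier reading the mean and median condition on recovery. Under the assumed scenarios they understate the difference by 24% to 54% with proportional hazards, and by all of it where only the proportion recovering differs. On the other reading, early losses are averaged as early recoveries. The size depends on how many patients fail to recover by Day 29, which the documents do not give. If nearly everyone recovers, it is small. The table should be corrected, but the endpoint's analysis is not invalid.

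**What to change.** In Table 14.2.5, replace Mean (SD) and Median (Min-Max) with:

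- N analysed (ITT) and n recovered
- n censored by reason: death, still hospitalized at Day 29, lost or withdrawn
- Kaplan-Meier median and quartiles with 95% CI, allowing an entry of not reached
- the log-rank p-value

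All rows should follow the 9.4.1 censoring rules. A Kaplan-Meier-based restricted mean to Day 29, with difference and 95% CI, is optional, since neither document plans one. If added, it should censor deaths at Day 29 and withdrawals at last observation. Any recovered-only summary that is kept should be labelled as descriptive, with no p-value beside it, and the footnote should define a recorded value. Removing the discharge clause from the title is cosmetic, because SAP Table 4 equates discharge with score 1 or 2, which is the recovery event.

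The cost is one revised shell and standard survival output, with no new data.
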